## 2. SYNOPSIS

Protocol Number: XSGP-301	
G-PEN™ (GLUCAGON INJECTION) COMPARED TO LILLY GLUCAGON (GLUCAGON FOR INJECTION [rDNA ORIGIN]) FOR INDUCED HYPOGLYCEMIA RESCUE IN ADULT PATIENTS WITH T1DM: A PHASE 3, MULTI-CENTER, RANDOMIZED, BLINDED, 2-WAY CROSSOVER STUDY TO EVALUATE EFFICACY AND SAFETY	
Principal Investigator:	Each participating clinical site will nominate a physician who, based on training and experience, will serve as principal investigator for that site.
IND:	115091
Project phase:	Phase 3
Compound(s):	G-Pen™ (glucagon injection) Lilly Glucagon for Injection (rDNA origin)
Objectives:	
 
1. To demonstrate the efficacy (return to plasma glucose >70.0 mg/dL) of G-Pen™ (glucagon injection) 1 mg (test) to be non-inferior to Lilly Glucagon (glucagon for injection [rDNA origin]) 1 mg (reference), in T1D patients in a state of insulin-induced hypoglycemia.
 
2. To compare the pharmacodynamic characteristics of G-Pen™ (glucagon injection) 1 mg (test) versus Lilly Glucagon (glucagon for injection [rDNA origin]) 1 mg (reference) in T1D patients who are in a state of insulin-induced hypoglycemia.
 
3. To describe and compare the hypoglycemia symptom relief of the two treatments.
 
4. To determine the safety and tolerability of G-Pen™ (glucagon injection) 1 mg (test) versus Lilly Glucagon (glucagon for injection [rDNA origin]) 1 mg (reference) in T1D patients in a state of induced hypoglycemia
 
5. To determine G-Pen™ (glucagon injection) 1 mg pharmacokinetics in the major ethnicities and races in the US: non-Hispanic Whites, Hispanics, and African-Americans.
 

Study design:	This is a randomized, blinded, two-way crossover comparative efficacy and safety inpatient study in patients with Type 1 diabetes mellitus (T1D). The study will involve two daytime clinical research center (CRC, or comparable setting) visits 7-28 days apart, with random assignment to receive G-Pen™ glucagon 1 mg during one session and Lilly Glucagon 1 mg during the other.
Study location:	Approximately 8 clinical research centers in North America.
Study duration:	The estimated duration of study participation for individual subjects is approximately 4 weeks. The estimated duration of the entire study is 5 months.

XSGP-301 Clinical Protocol  
G-Pen™ (glucagon injection)

Sample size:	Approximately 150 subjects are anticipated to be screened for this study to achieve the goal of 75 subjects completing the study with evaluable results for at least one treatment period. To allow for possible drop-outs, approximately 80 subjects may be randomized. Enrollment may be constrained based on ethnicity and race to achieve approximately 12 subjects in each of the following groups: non-Hispanic Whites, Hispanics, and African-Americans.
Subjects:	The study will include male or female patients with T1D between the ages of 18 and 75 years of age, inclusive, at Screening.
Inclusion Criteria:	
 
1. Males or females diagnosed with type 1 diabetes mellitus for at least 24 months.
 
2. Current usage of daily insulin treatment that includes having an assigned “correction factor” for managing hyperglycemia.
 
3. Age 18-75 years, inclusive.
 
4. Random serum C-peptide concentration < 0.5 ng/mL.
 
5. Willingness to follow all study procedures, including attending all clinic visits.
 
6. Subject has provided informed consent as evidenced by a signed/dated informed consent form completed before any trial-related activities occur.
 

Exclusion Criteria:	
 
1. Pregnant and/ or Nursing: For women of childbearing potential, there is a requirement for a negative urine pregnancy test and for agreement to use contraception and to refrain from breast feeding during the study, and for at least 1 month after the last does of study drug. Acceptable contraception includes birth control pill / patch / vaginal ring, Depo-Provera, Norplant, an IUD, the double barrier method (the woman uses a diaphragm and spermicide and the man uses a condom), or abstinence.
 
2. HbA1c >9.0% at Screening.
 
3. Renal insufficiency (serum creatinine greater than 3.0 mg/dL).
 
4. Serum ALT or AST equal to or greater than 3 times the upper limit of normal
 
5. Hepatic synthetic insufficiency as defined as a serum albumin of less than 3.0 g/dL; or serum bilirubin of over 2.0 mg/dL.
 
6. Hematocrit of less than or equal to 30%.
 
7. Mean of triplicate BP readings at Screening where SBP <90 or >140 mm Hg, and DBP <50 or >90 mm Hg.
 
8. Clinically significant ECG abnormalities.
 
9. Use of > 2.0 U/kg total insulin dose per day.
 
10. Inadequate bilateral venous access in both arms.
 
11. Congestive heart failure, NYHA class II, III or IV.
 
12. Active malignancy within 5 years from Screening, except basal cell or squamous cell skin cancers. History of breast cancer or malignant melanoma will be exclusionary.
 
13. Major surgical operation within 30 days prior to Screening.
 
14. Current seizure disorder.
 
15. Current bleeding disorder, treatment with warfarin, or platelet count below 50,000.
 

16. Personal history of pheochromocytoma or disorder with increased risk of pheochromocytoma (MEN 2, neurofibromatosis, or Von Hippel-Lindau disease).
17. History of insulinoma.
18. History of allergies to glucagon or glucagon-like products, or any history of significant hypersensitivity to glucagon or any related products or to any of the excipients (DMSO & trehalose) in the investigational formulation.
19. History of glycogen storage disease.
20. Subject tests positive for HIV, HCV or active HBV infection (HBsAg+) at Screening
21. Any concurrent illness, other than diabetes, that is not controlled by a stable therapeutic regimen.
22. Whole blood donation of 1 pint (500 mL) within 8 weeks prior to Screening. Donations of plasma, packed RBCs, platelets or quantities less than 500 mL are allowed at investigator discretion.
23. Active substance or alcohol abuse (more than 21 drinks/wk. for males or 14 drinks/wk. for females). Subjects reporting active marijuana use or testing positive for THC via rapid urine test will be allowed to participate in the study at the discretion of the investigator.
24. Administration of glucagon within 28 days of Screening.
25. Participation in other studies involving administration of an investigational drug or device within 30 days or 5 half-lives, whichever is longer, before Screening for the current study and during participation in the current study.
26. Any reason the investigator deems exclusionary.

Brief outline of treatments:

Subjects will complete the screening procedures up to 60 days before dosing to determine eligibility before enrollment to the treatment phase. Subjects will be instructed to fast from midnight prior to study visits and to dose with insulin as per their usual practice.

Eligible participants will undergo two episodes of insulin-induced hypoglycemia, and in random order will receive G-Pen™ glucagon 1 mg subcutaneously during one episode and Lilly glucagon 1 mg subcutaneously during the other episode. The procedure to evaluate the efficacy of the G-Pen™ glucagon consists of inducing hypoglycemia by an IV infusion of regular insulin diluted in normal saline.

For treatment visits, subjects will check into the clinical research center in the morning still fasting except for water.

Subjects will be randomized to receive either G-Pen™ (glucagon injection) or Lilly Glucagon blinded study medication to the following treatment sequence:

Group	Dose 1	Dose 2
1	G-Pen™ 1.0 mg	Lilly 1.0 mg
2	Lilly 1.0 mg	G-Pen™ 1.0 mg

**Note: The following is a summary only. Please see section 7.2 for a detailed description of the hypoglycemia induction procedures and see Section 10.2.1 for a detailed description of the treatment visit procedures.**

Subjects will have a catheter for IV insulin infusion inserted in one arm and another catheter for blood sampling inserted in the other. The arm used for blood sampling will be kept warm by use of a heating pad or similar device to increase blood flow to achieve “arterialized” samples.

Starting plasma glucose level will be determined by taking three measurements over 30 minutes. After 30 minutes:

1. Subjects will be given an initial IV bolus push dose of regular insulin:
  - a. Dose will be calculated based on the starting plasma glucose level and the subject’s self-reported glucose correction factor.
  - b. Additional bolus doses of insulin may be given as guided by the investigator’s experience if the trajectory of plasma glucose after 30 minutes is > 60 mg/dL. Late bolus doses (i.e., within 20 minutes of dosing) should be avoided.
2. Subjects will be given an IV infusion of regular insulin. The starting IV infusion rate will be based on a subject’s current use of insulin:
  - a. For subjects on insulin pump, the pump will be discontinued and IV insulin infusion will be started at 1.5x the recorded basal rate.
  - b. For subjects on long-acting injected insulin:
    - i. If the subject took their normal evening or morning dose before the visit, IV insulin infusion will be started at 1x the basal rate.\*
    - ii. If the subject did not take their normal evening or morning dose before the visit, IV insulin infusion will be started at 2x the basal rate.\*
  - c. Guided by experience, the investigator may adjust the IV insulin infusion rate at his discretion if the rate of glucose change after 30 minutes is < 1

mg/dL/min.

\* For injected insulin uses, the basal rate will be calculated by dividing the daily dose by 24 to calculate the amount of insulin on board in units/hour.

Plasma glucose measurements will be taken every 15 minutes while glucose is >80.0 mg/dL and at 5-minute intervals once plasma glucose is ≤ 80.0 mg/dL.

Once the initial plasma glucose measurement < 50.0 mg/dL is achieved, the IV insulin infusion will be stopped. During the 5-minute period after the IV insulin infusion has stopped, the glucose level is expected to continue to decrease by approximately 5 mg/dL due to the delayed effect of insulin. Once the confirmatory plasma glucose reading < 50.0 mg/dL is achieved 5 minutes later, subjects will be administered blinded study drug via the subcutaneous route in the upper arm, leg or abdomen.

Following dosing, plasma glucose will be monitored every 5 minutes until 90 minutes post-dosing. Additional blood samples will be collected at -5, 0, 10, 20, 30, 45, 60, 90, 120, 180 and 240 minutes and stored at -70C for determination of plasma glucagon and potentially insulin levels. After this, the subject will resume insulin pump therapy, if applicable, and will be given a meal. The subject can then leave the clinic after glucose concentration is confirmed to be between 70 and 180 mg/dL.

Subjects will complete a questionnaire regarding hypoglycemia symptoms at the start of the hypoglycemia induction period and periodically until 30 minutes post-treatment with glucagon. The hypoglycemia induction procedure is expected to elicit symptoms of a hypoglycemic response. However, the procedure is not expected to be of sufficient duration, or to generate such a low glucose concentration in the CNS that it will impair consciousness characteristic of severe hypoglycemia.

After a wash-out period of 7 to 28 days, subjects will return to the clinic and the study procedures will be repeated with each subject crossed over to the other treatment. After study-related procedures are performed on each of the treatment days, subjects will be discharged. A follow-up visit will be conducted 3-14 days following administration of the final dose as a safety check.

Tolerability will be assessed by comparing adverse event reports between the groups. In addition, subjects will complete questionnaires concerning injection site discomfort. An investigator will use modified Draize scales to evaluate the injection sites following each administration.

Data management and statistical analysis:

Data will be entered into an electronic Case Report Form by site personnel. Data will be monitored at on-site visits by Xeris personnel or by a CRO acting as Xeris' agent.

The primary comparison will be performed using the intent-to treat (ITT) cohort defined as all subjects randomized to one of the two sequence groups: G-Pen followed by control, or control followed by G-Pen. A failure is recorded if the subject's plasma glucose fails to rise above 70.0 mg/dL within 30 minutes of the start of therapy.

The following scoring system will be applied to all subjects in the ITT cohort. If a G-Pen failure is observed then the treatment failure score = 1. Similarly, the failure score = 1 if a control failure is observed. If the treatment outcome is missing, then the treatment failure score = 0.2. A missing control outcome yields a control failure score = 0.1. An observed success for both groups yields

	
a failure score = 0.
 
The G-Pen acceptance criterion will be based on the sample mean of the treatment minus control failure scores from each subject in the ITT population. If <math>D_{ht}</math> is the sample mean and SE is the estimated standard error of the subject treatment minus control failure scores, then the G-Pen will be accepted provided:
 
<math>D_{ht} + 2.6 SE</math> is less than or equal to 0.1.
 
This criterion, particularly the value 2.6, came from Monte-Carlo simulations from selected scenarios, where the population G-Pen failure rate exceeded the control rate by 0.1. Under these circumstances the rate of G-Pen acceptance was found to be within 0.025 using this criterion. The acceptance criterion for the G-Pen in this study will be that the total difference in failures, G-Pen minus Control (i.e., Lilly Comparator), shall not exceed 3 and the total number of failures for the G-Pen shall not exceed 4, after the 75th evaluable subject completes both treatment periods.
 
If the total number of subjects with criterion failures (counted in a blinded fashion) exceeds 4, a monitoring statistician not otherwise involved with study conduct may provide an unblinded determination of the distribution by treatment group for futility only, and communicate a finding of futility (or continue to conclusion) to Xeris' upper management for further decisions, while the study team remains blinded. Success will not be tested and no penalty for this futility only check is planned.

Sample Size Determination:	
Using the above criterion, a sample size of 75 subjects yields probabilities of G-Pen acceptance of over 90% if the population failure rates of G-Pen and control are equal, and the rate of missing observations is within 15%. These results were obtained using Monte Carlo simulations with G-Pen and control total failure rates up to 5%, and with G-Pen success Control failure, or G-Pen failure Control success within 1%.
 
Patients may be recruited at approximately 8 clinical sites with a goal of no single center accounting for > 20% of the total sample.

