## **9. STUDY TREATMENTS**

### **9.1. Allocation to Treatment**

Subjects will be randomized to one of the 2 treatment groups to receive the appropriate sequence of blinded study medication (see [Table 3](#)). Approximately 80 patients will be randomized with a goal of completing 75 patients, or roughly 37-38 patients per group. If there are a large number of subjects who are randomized but fail to receive either study drug, compensatory enrollment will be utilized to achieve at least 75 evaluable subjects. Each subject will receive a single subcutaneous injection on each of the two (2) treatment days, with a period of 7-28 days between doses.

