#### 13.1.2. Sample Size Calculation:

Using the above criterion, a sample size of 75 subjects yields probabilities of G-Pen acceptance of over 90% if the population failure rates of G-Pen and control are equal, and the rate of missing observations is within 15%. These results were obtained using Monte Carlo simulations with G-Pen and control total failure rates up to 5%, and with G-Pen success Control failure, or G-Pen failure Control success within 1%.

The power and type 1 error bounds were obtained from a simulation model using a 3x3 table of outcomes for G-Pen and control. The three outcomes for each were Success, Failure, and Missing. Probabilities were assigned to each of the 9 cells, with the missing outcome being

stochastically independent of the Success, Failure outcome combinations. Also the failure score difference, G-Pen minus control, was assigned to each of the nine cells. To simulate one replicate of the study, 75 independent draws were made from the multinomial distribution determined by the probabilities from the 9 cells, and the sample mean, estimated standard error were computed. The G-pen acceptance criterion was applied and either a 0 (G-pen failed) or 1 (G-pen accepted) was recorded. This was repeated 10,000 times to obtain the estimated probability of G-pen acceptance under the conditions defined by the cell probabilities. The simulations were performed using R version 3.1.2 (2014-10-31).

Approximately 80 subjects will be randomized at approximately 8 clinical sites with a goal of no single center accounting for > 20% of the total randomization.

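### The target of 75 subjects is defined in more than one way, and the enrolment plan does not secure the 75 both-period completers at which the synopsis count rule is to be read

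*Combined protocol and SAP*

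**What the plan says.** Four places in the protocol give or use the number 75.

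- **Synopsis, Sample size.** The aim is a "goal of 75 subjects completing the study with evaluable results for at least one treatment period". To allow for drop-outs, "approximately 80 subjects may be randomized".
- **Synopsis, Data management and statistical analysis.** After the scored criterion (mean failure-score difference D plus 2.6 SE at most 0.1), a second acceptance rule follows: the G-Pen minus control difference in failures "shall not exceed 3 and the total number of failures for the G-Pen shall not exceed 4". It is read after the 75th "evaluable subject completes both treatment periods".
- **Section 9.1.** "Approximately 80 patients will be randomized with a goal of completing 75 patients, or roughly 37-38 patients per group". Extra enrolment is conditional: "If there are a large number of subjects who are randomized but fail to receive either study drug", then "compensatory enrollment will be utilized to achieve at least 75 evaluable subjects". Evaluable is not defined.
- **Section 13.1.2.** The simulation draws 75 subjects from a 3x3 table in which each treatment outcome is Success, Failure or Missing. Power is over 90% provided "the rate of missing observations is within 15" per cent.

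Section 13.1 excludes from the ITT analysis subjects who fail eligibility or receive neither drug. It keeps subjects with one missing outcome, scoring a missing G-Pen result 0.2 and a missing control result 0.1. Section 13.1.1 contains only the scored rule.

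**The concern.** A subject with a usable result in one period and none in the other can count toward the first synopsis target but not toward 75 complete pairs. No section says which count closes enrolment, which one triggers the analysis, or what happens when the first is met and the second is not. Section 9.1 does not clearly replace one-period subjects. Its wording about failing to receive either drug most naturally means neither drug, which is also the wording of the ITT exclusion in Section 13.1.

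The synopsis presents the count rule as the acceptance criterion for the study, so its reading point matters. Its limits of 3 and 4 are fixed numbers, and what they imply depends on how many pairs lie behind them. Reading the result at the 75th completer also sits badly with a primary analysis of all ITT subjects, since others may still be in the study at that moment.

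**Working it through.** **1. The plan's own power figure.** Inputs from Sections 13.1 to 13.1.2: n = 75; missingness independent of outcome; missing scores 0.2 and 0.1; acceptance if D + 2.6 SE ≤ 0.1; equal failure rates; 1% discordance in each direction. The 15% missing rate is taken as applying to each treatment outcome, which the text does not specify. Re-running the simulation gives this power:

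| Failure rate, each treatment | No missing | 15% missing |
|---|---|---|
| 1% | 0.993 | 0.952 |
| 5% | 0.993 | 0.907 |

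The stated figure of over 90% is reproduced. One of the 75 here is a subject whose outcomes may be missing, so this power does not rest on 75 complete pairs.

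**2. Chance of 75 complete pairs from 80 randomized.** Let q be the share of subjects lacking one or both outcomes, with losses independent and one-period subjects not replaced. The chance is P(X ≥ 75) with X ~ Binomial(80, 1 − q). The documents give no q. Going from 80 to 75 implies 5/80 = 6.25%.

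| q | Expected pairs, 80 × (1 − q) | P(at least 75 pairs) |
|---|---|---|
| 4% | 76.8 | 0.90 |
| 5% | 76 | 0.79 |
| 6.25% | 75 | 0.62 |
| 7.5% | 74 | 0.44 |
| 10% | 72 | 0.18 |

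**3. Why the number of pairs matters to the count rule.** Take 3 G-Pen-only failures, no other failures and nothing missing. Then D = 3/n and SE² = (3 − 9/n) / [(n − 1)n].

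- n = 75: D = 0.0400, SE² = 2.88 / (74 × 75) = 0.000519, SE = 0.0228, so D + 2.6 SE = 0.0992 (accept).
- n = 74: 0.1006 (reject).
- n = 70: 0.1063 (reject).

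In this simple case the allowance of 3 agrees with the scored rule at 75 pairs but not below. Agreement at 75 is not complete either. Four G-Pen-only failures and one control-only failure meet both limits (difference 3, G-Pen total 4), yet D + 2.6 SE = 0.0400 + 2.6 × √[(5 − 9/75) / (74 × 75)] = 0.1171 (reject).

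**4. False acceptance under the count rule.** At a true excess of 0.10 with no control failures, the rule reduces to at most 3 G-Pen failures, so the probability is P(Y ≤ 3) with Y ~ Binomial(n, 0.10). This is 0.035 at 80 pairs, 0.050 at 75 and 0.082 at 68. With a 5% control failure rate, all shared with G-Pen, it is about 0.007 at 75 and 0.015 at 68. The level depends on the control rate, but in both cases the rule becomes more lenient as pairs are lost.

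**The case against.** **Softer reading of the synopsis.** The first target speaks of subjects completing the study, so a subject who leaves after one period arguably does not count. The second may be only a timing trigger: the 75th evaluable subject has attended both visits. The two then largely agree. This reading is possible and lowers the seriousness of the point. It still leaves evaluable undefined and does not secure 75 pairs of outcomes.

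**The both-periods condition belongs to one sentence.** It appears only with the count rule in the synopsis; Section 13.1.1 does not use it. This stands. A reader might infer that the trial is underpowered if pairs are lost, but step 1 shows that the stated power already allows for missing outcomes.

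**Losses are mitigated.** Failed inductions are rescheduled (Section 10.2.1), missed visits are pursued (Section 10.3), and 80 is approximate rather than a cap. So it would be wrong to say that the decision point cannot be reached. A reader might also take the 15% in Section 13.1.2 as the expected loss, at which the chance of 75 pairs from 80 is 1.4%. It is the upper limit of the simulated range, not a forecast.

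**Choice of final sample size.** A reader might infer that the sponsor would choose between further enrolment and early reading in the light of the results. The documents do not support this. Section 13.5 describes a blinded pooled count, with any unblinding left to a separate statistician and for futility only.

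**Later detail.** Section 13.5 leaves specifics to a SAP, whose text does not appear in the document reviewed. It might define evaluable, but the synopsis and Section 9.1 would still have to be made consistent with it.

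**Conclusion.** The inconsistency is real and worth correcting, but limited. The plan uses 75 for at least two different counts, and the enrolment described does not assure 75 complete pairs: about 62% at the implied 6.25% loss, with a range from 90% at 4% to 18% at 10%. These figures assume exactly 80 randomized, independent losses and no replacement of one-period subjects. The loss rates are assumptions, because the documents state none.

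The scored analysis in Section 13.1.1 and its stated power are unaffected. What is left unsettled is when the synopsis count rule is read and how many subjects it is read on. Its fixed limits do not carry over to fewer than 75 pairs. Whether the multiplier 2.6 holds the 0.025 error bound in every setting is a separate question that this point does not settle.

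**What to change.** 1. Use one definition of the 75 in the Synopsis (both places), Section 9.1 and Section 13.1.2: 75 ITT subjects, meaning eligible, randomized and given at least one study drug, with missing outcomes scored as in Section 13.1. This fits the simulation better than requiring one evaluable period, because the 3x3 table includes a cell with both outcomes missing.
2. In the synopsis, replace the trigger at the 75th both-period completer with: after the last randomized subject has completed or left the study.
3. In the same place, base acceptance on D + 2.6 SE ≤ 0.1 in all ITT subjects. Moving the trigger alone would leave fixed limits of 3 and 4 on a variable number of subjects.
4. Remove those limits, or label them as illustrating the scored rule at 75 complete pairs. Removal is cleaner, since the two rules can disagree even there.

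Cost: wording in the Synopsis and Sections 9.1 and 13.1.2. No extra patients.

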#### 13.1.1. Primary Endpoint:

The G-pen acceptance criterion will be based on the sample mean of the treatment minus control failure scores from each subject in the ITT population. If  $D_{ht}$  is the sample mean of the G-Pen minus control failure difference, and SE is the estimated standard error of  $D_{ht}$  (square root of the estimated G-Pen minus control variance divided by the sample size), then the G-Pen will be accepted provided:

$$D_{ht} + 2.6 SE \leq 0.1.$$

This criterion, particularly the value 2.6, came from Monte-Carlo simulations from selected scenarios where the population G-Pen failure rate exceeded the control rate by 0.1. Under these circumstances the rate of G-Pen acceptance was found to be within 0.025 using this criterion, with missing data rates within 15%. This bound of 0.025 on the type 1 error rate was observed for control failure rates up to 5%. Monte Carlo simulation rather than asymptotic normality is necessary because an observed failure from either G-Pen or control is expected to be low, less than 5%.

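### The Synopsis gives two different acceptance rules for the primary comparison, does not say how they combine, and Section 13.1.1 contains only one of them

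*Combined protocol and SAP*

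**What the plan says.** **Synopsis, data management and statistical analysis.** Each ITT subject gets a G-Pen and a control failure score: 1 for an observed failure, 0 for an observed success, and 0.2 (G-Pen) or 0.1 (control) for a missing outcome. G-Pen is accepted if Dht + 2.6 SE ≤ 0.1. Later in the same paragraph the acceptance criterion is stated again, as a limit on counts: the excess of G-Pen over control failures "shall not exceed 3 and the total number of failures for the G-Pen shall not exceed 4", judged once the 75th "evaluable subject completes both treatment periods". No connecting word or order of precedence links the two.

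**Section 13.1.1** has the score rule alone: "The G-pen acceptance criterion will be based on the sample mean of the treatment minus control failure scores from each subject in the ITT population". On its error rate it adds: "This bound of 0.025 on the type 1 error rate was observed for control failure rates up to 5" per cent.

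**Power.** Section 13.1.2 says that "a sample size of 75 subjects yields probabilities of G-Pen acceptance of over 90" per cent, for equal failure rates up to 5%, discordant cells within 1% and missing data within 15%. The Synopsis makes the same claim, opening with "Using the above criterion, a sample size of 75 subjects yields probabilities of G-Pen acceptance of over 90" per cent. There, the criterion immediately above is the count rule.

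**The 75 subjects.** The Synopsis sample-size entry aims for "75 subjects completing the study with evaluable results for at least one treatment period", whereas the count rule waits for both periods. Section 9.1 says that "compensatory enrollment will be utilized to achieve at least 75 evaluable subjects" without defining the term.

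Section 13.5 leaves further detail to a separate SAP. Nothing in the supplied text settles which rule governs.

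**The concern.** A non-inferiority trial needs one success rule fixed before the data are seen. Here two sentences in one paragraph each claim that role. They use different data (ITT with scored missing outcomes, against 75 evaluable subjects with both periods complete) and different statistics. If they disagree, the primary conclusion depends on which sentence is applied afterwards.

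The stated type 1 error and power were simulated for the score rule. No error rate is given for the count rule, for requiring both rules, or for accepting on either.

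The futility look is also affected. It may be triggered once more than 4 subjects have failures. Five subjects failing on both drugs would already breach the count rule's cap on G-Pen failures, yet they are fully compatible with success under the score rule. The monitoring statistician therefore needs to know which rule applies during the trial.

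**Working it through.** **Notation.** With n = 75 complete pairs, let a = G-Pen-only failures, b = control-only failures, c = failures on both drugs.

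- Score rule: D = (a − b)/n; variance = (a + b − nD²)/(n − 1); SE = √(variance/n). Accept if D + 2.6 SE ≤ 0.1. The count c does not enter.
- Count rule: accept if a − b ≤ 3 and a + c ≤ 4.

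**The plan's own figure.** Simulating the Section 13.1.2 model (3×3 table, missingness independent of outcome, 15% missing per period as an assumption, 200,000 replicates), the lowest score-rule acceptance over the stated range was 0.9075. This was at 5% failures, 1% discordance each way and 15% missing. The claim of over 90% therefore reproduces for the score rule.

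**Opposite verdicts on complete data.** For a = 4, b = 1: D = 3/75 = 0.0400; variance = (5 − 75 × 0.0016)/74 = 0.0659; SE = 0.0297; bound = 0.0400 + 2.6 × 0.0297 = 0.117.

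| a | b | c | Score bound | Score rule | Count rule |
|---|---|---|---|---|---|
| 4 | 1 | 0 | 0.117 | reject | accept |
| 4 | 2 | 0 | 0.112 | reject | accept |
| 4 | 3 | 0 | 0.106 | reject | accept |
| 0 | 0 | 5 | 0 | accept | reject |
| 3 | 0 | 2 | 0.0992 | accept | reject |

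Using n instead of n − 1 in the variance changes none of these verdicts.

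**With missing outcomes.** Take 80 ITT subjects: 75 complete both periods, 3 of them G-Pen-only failures, and 5 have a missing G-Pen outcome with control success. D = (3 + 5 × 0.2)/80 = 0.0500, SE = 0.0218, bound = 0.1066. The score rule rejects. The count rule (difference 3, G-Pen failures 3) accepts.

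**Power.** Exact multinomial sums over (a, b, c), no missing data, equal rates, 1% G-Pen-only, 1% control-only, remainder failing on both:

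| Failure rate | Score rule | Count rule | Both required | Rules disagree |
|---|---|---|---|---|
| 1% | 99.3% | 99.6% | 99.3% | 0.3% |
| 2% | 99.3% | 98.1% | 98.0% | 1.5% |
| 3% | 99.3% | 92.4% | 92.4% | 7.0% |
| 4% | 99.3% | 81.8% | 81.8% | 17.5% |
| 5% | 99.3% | 67.9% | 67.9% | 31.5% |

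From 2% upwards, disagreement is mostly the score rule accepting and the count rule rejecting; at 3% and above it is nearly all of this kind. The reverse is at most 0.3%, at 1% failures. With 15% missing and 5% failures, counting observed failures only for the count rule, simulation gives 0.908 (score), 0.785 (count) and 0.750 (both).

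**False acceptance at a true excess of 0.10.** Exact, no missing data, a-rate = 0.10 + b-rate:

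| Control failures | Score rule | Count rule | Either rule |
|---|---|---|---|
| None | 5.0% | 5.0% | 5.0% |
| 1%, all control-only | 2.9% | 5.4% | 5.4% |
| 5%, of which 1% control-only | 2.9% | 0.8% | 3.0% |

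Over control rates of 0 to 2% the count rule gives 3.1 to 5.7%. From 3% upwards it is at or below 2.5%.

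**The case against.** The strongest benign reading is that the count rule is meant as shorthand for the score rule. With complete data and no control-only failures, 3 G-Pen-only failures give a bound of 0.0992 (accept) and 4 give 0.1212 (reject), so a limit of 3 on the difference matches. That explains where the 3 may come from. The match fails once there are control-only failures or missing outcomes, and the cap of 4 G-Pen failures does not follow from the score rule.

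Section 13.1.1 is unambiguous, and the power claim, with its allowance for missing data, evidently belongs to the score rule. This stands as a reading of intent. It does not remove the second criterion from the Synopsis or say that Section 13 prevails, and a SAP outside the supplied text cannot be assumed to do so.

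The larger figures come from the edge of the planning range. Disagreement is only 0.3% and 1.5% of trials at 1 and 2% failures. The 5.4% against 2.9% comparison is the largest gap among the scenarios examined. If all control failures are concordant, accepting on either rule is no more lenient than the score rule (5.0% for both). These limits are fair, but rates up to 5% are the plan's own range.

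The two descriptions of the 75 subjects could be reconciled by reading completion of both periods as a timing condition. Even so, the enrolment target and the decision point are not the same number of subjects.

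Finally, the score rule itself exceeds 0.025 in some complete-data scenarios, so retaining it does not cure every error-rate problem. That is true and is a separate matter.

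**Conclusion.** The point holds and should be corrected before the data are analysed. The Synopsis states two acceptance rules that are neither joined nor ranked. They can contradict each other in both directions, and only one appears in Section 13.1.1.

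If the count rule binds, alone or jointly, power falls below the stated 90% at 4 and 5% failures (81.8% and 67.9%). If either rule may be used, false acceptance can reach 5.4% where the score rule alone gives 2.9%.

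Unless stated otherwise, the figures assume 75 complete pairs. The power figures also assume equal failure rates and 1% discordance each way. The opposite verdicts in the worked tables depend on no assumption about failure rates.

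**What to change.** State in both the Synopsis and Section 13.1.1 that the score rule on the ITT cohort is the sole acceptance criterion. Delete the count sentence, or label it non-binding, for example as a guide for the futility check. Name the score rule explicitly in the Synopsis power statement. Use one definition of the 75 evaluable subjects in the Synopsis sample-size entry, the Synopsis analysis text and Section 9.1.

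The statistical cost is the loss of the cap of 4 G-Pen failures. Where control failures are mostly concordant, that cap made acceptance stricter: 0.8% against 2.9% false acceptance at 5% control failures with 1% control-only. If the sponsor wants both rules to hold, the plan should say so and restate type 1 error and power for the joint rule (about 68% power at 5% failures without missing data).

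The preferred fix changes wording only, with no new data or procedures, but as a protocol modification it needs the IRB review described in Section 18.1. The joint rule would also need the simulations rerun.
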